## 7. Description of intended clinical benefits to patients. Clinical outcome parameters.

It is expected that, compared to conventional clinical management without a clinical decision support system, naevia will increase the number of appropriate recommendations and significantly reduce the number of inappropriate and absent recommendations in all the domains analyzed.

Dilemma Solutions S.L.	CHAPTER 06-1C	TD01-06-1C Ver.: 01 2025/03/03
	CLINICAL EVALUATION PLAN (CEP)	Page 12 of 38

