### Evidence from clinical evaluation/investigations

- Software enables to provide recommendations and suggestions for knowledge related to diagnosis, prognosis and/or treatment: scientific literature confirms that SW system functions and features are aligned with current user requirements as described in relevant publications and as included in the DUE.

Dilemma Solutions S.L.	CHAPTER 06-1C	TD01-06-1C Ver.: 01 2025/03/03
	CLINICAL EVALUATION PLAN (CEP)	Page 13 of 38

- Increase of appropriate recommendations: number of appropriate recommendations – an observational, single-centre study consisting on a clinical validation of a CDSS applied to retrospective clinical cases of cardiology patients with valvular heart disease, shall confirm an increase in the number of appropriate recommendations by by a factor of three over the recommendations generated with general management without the support system.
- Inappropriate recommendations: number of inappropriate recommendations – an observational, single-centre study consisting on a clinical validation of a CDSS applied to retrospective clinical cases of cardiology patients with valvular heart disease, shall confirm that naevia medical, compared to conventional management, is able to reduce the number of inappropriate and mising recommendations based on scientific evidence in the diagnostic and therapeutic areas.
- Concordance between expert evaluators:
  - o The analysis of the degree of agreement/disagreement in the different domains, evaluated using a Likert scale, analysed using ordinal regression (Joshi, Kale et al. 2015). Response options: 1. Strongly disagree, 2. Disagree, 3. Neither agree nor disagree, 4. Agree, 5. Strongly agree.
  - o The panel's agreement with the CDSS was very high, with a mean Likert scale score above 4 in all domains (STD: 4.53, LTD: 4.68, CMT: 4.58, ITI: 4.62). The probability of strongly agreeing was significantly higher than the probability any of the other categories (z.ratio (5|1)= 30.88, p-value< 0.001, z.ratio (5|2)= 31.67, p-value < 0.001, z.ratio (5|3) = 30.21, p-value< 0.001, z.ratio (5|4)= 22.54, p-value< 0.001).

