**Table 1 – Naevia Medical – Indicative List of Clinical Safety and Performance Parameters and Quantitative Measures**

Parameter / Outcome	Quantitative Measure of Performance	Source / Level of Evidence Required	
Performance of Naevia medical to provide healthcare professionals with recommendations and suggestions for knowledge related to diagnosis, prognosis and/or treatment			
Software enables to provide recommendations and suggestions for knowledge related to diagnosis, prognosis and/or treatment	
Goal: all basic key characteristics of CDSS are supported and all supported characteristics work correctly and as expected.
 
[references to sources]
 
*EN ISO 62304 – Medical device software – Software life-cycle processes
 
EN 82304 – Health Software – Part 1: General requirements for product Safety
	Preclinical	
Accepted if using the system functions and features, users are able to get recommendations and suggestions for knowledge related to diagnosis, prognosis and/or treatment.
 
 
- V&V per EN ISO 62304 and install validation. All tests provide recommendations and suggestions and thus CDSS is verified by all tests.
 
- V&V per EN 82304 and install validation. All tests provide recommendations and suggestions and thus CDSS is verified by all tests.
 
- Usability testing of the software by representative users to successfully provides recommendations and suggestions for knowledge related to diagnosis, prognosis and/or treatment.
 

		Clinical	
Accepted if system features cover user needs for getting recommendations and suggestions for knowledge related to diagnosis, prognosis and/or treatment aligned with the tools required for medical diagnosis support and using the system functions and features, users successfully use CDSS to make clinical decisions regarding diagnosis, prognosis and/or treatment.
 
 
- V&V per EN ISO 62304 and install validation. All tests provide recommendations and suggestions and thus CDSS is verified by all tests*.
 
- V&V per EN 82304 and install validation. All tests provide recommendations and suggestions and thus CDSS is verified by all tests.
 

Dilemma Solutions S.L.	CHAPTER 06-1C	TD01-06-1C Ver.: 01 2025/03/03
	CLINICAL EVALUATION PLAN (CEP)	Page 25 of 38

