	43(7), https://doi.org/10.1093/eurheartj/ehab395	561-632.		
Appropriate recommendations	Increase the number of appropriate recommendations by a factor of three	Clinical	-	An observational study consisting on a clinical validation of a CDSS applied to retrospective clinical cases of cardiac patients with valvular heart disease, shall confirm an increase in the number of appropriate recommendations by a factor of three over the recommendations generated with conventional management without the support system.
Inappropriate recommendations	Reduction of inappropriate recommendations	Clinical	-	An observational study consisting on a clinical validation of a CDSS applied to retrospective clinical cases of cardiac patients with valvular heart disease, shall confirm that Naevia medical, compared to conventional management, is able to significantly decreased the number of inappropriate and missing recommendations in all the domains analyzed.

Dilemma Solutions S.L.	CHAPTER 06-1C	TD01-06-1C Ver.: 01 2025/03/03
	CLINICAL EVALUATION PLAN (CEP)	Page 27 of 38

Concordance between expert evaluators	Professionals agreement [reference to sources]  *Joshi, A., S. Kale, S. Chandel and D. K. Pal (2015). "Likert Scale: Explored and Explained." Current Journal of Applied Science and Technology 7: 396-403.	Clinical	
 
- The panel's agreement with the CDSS was very high, with a mean Likert scale score above 4 in all domains (STD: 4.53, LTD: 4.68, CMT: 4.58, ITI: 4.62). The probability of strongly agreeing was significantly higher than the probability any of the other categories (z.ratio (5 1)= 30.88, p-value< 0.001, z.ratio (5 2)= 31.67, p-value < 0.001, z.ratio (5 3) = 30.21, p-value< 0.001, z.ratio (5 4)= 22.54, p-value< 0.001).
 
-
 

Safety of Naevia medical			

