### Statistical analysis plan

The study is designed as a pre-test-post-test evaluation of a randomly assigned group, using a longitudinal repeated measures approach and retrospective validation. The clinical management of the included cases will be retrospectively evaluated by a panel of 3 experts with access to the most updated guidelines. For each case, the panel will perform the assessment at baseline (without CDSS) and repeated the assessment after the activation of the CDSS. The experts will label all the given clinical recommendations as appropriate or inappropriate and will identify the ones that are missing but relevant for clinical decision making. Finally, they will state their grade of agreement with the CDSS suggestions on a five-level Likert scale. The number and percentage of appropriate, inappropriate and missing relevant recommendations in each scenario will be considered for analysis.

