### **Analysis of the amount and quality of recommendations**

The impact of the CDSS activation on the recommendations will be assessed by analyzing the *number* of recommendations (appropriate, inappropriate, missing) per patient. The mean number of appropriate, inappropriate, and missing relevant recommendations generated per patient will be compared before and after the CDSS activation. Descriptive statistics, including mean (standard deviation [SD]), median (interquartile range [IQR]), and range, will be reported for these counts. To statistically compare the distributions of the *number* of appropriate, inappropriate, and missing recommendations per patient before and after CDSS implementation, the Wilcoxon signed-rank test will be applied.

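### Table 1 demands a significant decrease in every domain, but the SAP plans no domain analysis; the required increase is also stated two ways and gets no confidence interval

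*SAP*

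**What the plan says.** **Decrease in inappropriate and missing recommendations.** Table 1 in Protocol section 11 says the study shall confirm that the device "is able to significantly decreased the number of inappropriate and missing recommendations in all the domains analyzed". Section 7 expects it to "significantly reduce the number of inappropriate and absent recommendations in all the domains analyzed". Section 7.1 words the criterion more weakly: a reduction in "recommendations based on scientific evidence in the diagnostic and therapeutic areas", without requiring significance or every domain.

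**Planned analysis.** The SAP's design paragraph says: "The number and percentage of appropriate, inappropriate and missing relevant recommendations in each scenario will be considered for analysis". Its analysis section adds "Descriptive statistics, including mean (standard deviation [SD]), median (interquartile range [IQR]), and range, will be reported for these counts". The only test it names is in this clause: "recommendations per patient before and after CDSS implementation, the Wilcoxon signed-rank test will be applied". Neither part of the SAP mentions domains.

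**Domains.** The Protocol gives labels (STD, LTD, CMT, ITI) only with the agreement scores, introduced as "The analysis of the degree of agreement/disagreement in the different domains, evaluated using a Likert scale". No list of domains is given for the counts.

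**Increase in appropriate recommendations.** Section 14 (Primary and Secondary Outcomes) calls a 15% increase clinically beneficial and gives a percentage-increase formula. Section 7.1 and Table 1 say the study shall confirm an increase by a factor of three. The SAP names no threshold, ratio or confidence interval.

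**The concern.** A test on each patient's total can be clearly significant while one domain stays flat or deteriorates. It therefore cannot support a claim about every domain, and the SAP plans nothing else that could. The risk is that the overall p-value is reported as if it met the Table 1 criterion. This matters because section 11 makes acceptability of the benefit-risk ratio depend on the parameters in that table.

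For appropriate recommendations, two thresholds for one outcome allow opposite conclusions from the same estimate. The signed-rank p-value addresses whether there is any shift, so it settles neither threshold. Without an interval, an estimate close to whichever threshold applies cannot be judged.

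**Working it through.** **Inputs from the documents.** n = 101 (section 14, main clinical investigation); four domain labels, given only with the agreement scores; thresholds of 15% and a factor of three. The sample size cannot be reproduced, because no significance level, power, SD or baseline count is given.

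**Assumptions.** Two-sided 5% level, one outcome, and Poisson baseline counts with the same mean in each domain (0.1, 0.25, 0.5 or 1.0). Before and after counts are either independent or linked. In the linked case, halving removes each of a patient's own items with probability one half. An unchanged domain keeps half its items and gains as many new ones on average, and a worsening domain keeps all its items and gains half as many again.

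**Step 1: can the overall test stand in for the domain criterion?** Simulation with 1,500 replicates per cell; signed-rank test with zero differences dropped and a tie-corrected normal approximation; success means p < 0.05 in the direction of a decrease. Entries are the percentage of trials at baseline means 0.1 / 0.25 / 0.5 / 1.0.

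| True effect | Overall test, independent | Overall test, linked | Every domain significant |
|---|---|---|---|
| 4 domains: 3 halved, 1 unchanged | 45 / 84 / 99 / 100 | 87 / 100 / 100 / 100 | 0–4 |
| 4 domains: 3 halved, 1 up 50% | 20 / 46 / 75 / 95 | 64 / 96 / 100 / 100 | 0 |
| 2 areas: 1 halved, 1 unchanged | 13 / 25 / 46 / 75 | 25 / 55 / 83 / 98 | 1–3 |

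The last column is low by construction, since an unchanged domain passes only about 2.5% of the time. The informative columns are those for the overall test. With two areas, one halved and one up 50%, the changes cancel; the overall test is then significant in only 2–3% of trials and the problem does not arise.

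**Step 2: how far apart are the thresholds?** The section 14 formula is (post − baseline) / baseline × 100. A 15% increase is a ratio of 1.15. Three times baseline is (3 − 1) / 1 × 100 = +200%, a ratio of 3.0. Any ratio from 1.15 up to, but not including, 3 meets one threshold and fails the other.

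**Step 3: what would an interval add?** For independent Poisson counts with baseline mean m and observed ratio R, the 95% interval is R × exp(±1.96 × √[1/(101m) + 1/(101mR)]).

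- R = 1.15, m = 6: 1.15 × exp(±1.96 × √[1/606 + 1/696.9]) = 1.031 to 1.282, or +3% to +28%.
- R = 1.15 at m = 2, 4 and 10: −5% to +39%, +1% to +31%, and +6% to +25%.
- R = 1.15, m = 6, with 80% of baseline items shared (covariance 0.8 × 6 = 4.8): subtract 2 × 4.8 / (101 × 6 × 6.9) under the root, giving 1.088 to 1.215.
- R = 2.8, m = 4: 2.8 × exp(±1.96 × √[1/404 + 1/1131.2]) = 2.50 to 3.14, which includes 3.
- R = 2.0, m = 4: 1.77 to 2.25. This clearly misses a factor of three, as the point estimate already shows.

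**The case against.** The SAP fits the main objective in section 14, which names no domains, and the signed-rank test suits paired counts. Table 1 is titled an "Indicative List of Clinical Safety and Performance Parameters and Quantitative Measures", and section 7.1 states the decrease more weakly. Section 14 cites a separate investigation plan that was not supplied. Domain-level agreement results already appear in the Protocol although the SAP gives no method for them, so some analysis exists outside this text. The 15% may be a relevance threshold and the factor of three a performance target. No supplied text requires proof that a threshold is exceeded. The simulated rates rest on assumed counts.

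Much of this stands as a limit on scope. The conclusion covers the supplied documents only, the overall test should stay, and the simulation shows what can happen, not how likely it is here. The planned means and the section 14 formula would expose a clear miss without an interval.

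The two contradictions remain. The Table 1 row still says the study shall confirm the result, and its title does not undo that. The differing wordings add to the inconsistency. If 15% and a factor of three serve different purposes, the documents need to say which one decides success.

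**Conclusion.** The point holds for the documents as supplied and should be fixed. The planned analysis does not address the Table 1 criterion of a significant decrease in all domains. With three of four domains halved and the fourth 50% worse, the overall test would still succeed in 20–95% of trials (independent counts) or 64–100% (linked), over assumed baseline means of 0.1 to 1.0 per domain. The documents give neither the counts nor the before–after correlation, so the range cannot be narrowed.

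The two thresholds, +15% and +200%, conflict for any ratio from 1.15 to just below 3. This takes the factor of three to mean three times baseline. The missing interval is the lesser issue, because it matters only when the estimate lies near the threshold.

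**What to change.** 1. Reconcile the 15% in section 14 with the factor of three in section 7.1 and Table 1, and name one threshold. Settle one wording of the decrease criterion and one list of domains for the counts.
2. For inappropriate and for missing recommendations, run the same signed-rank test in each listed domain, with the paired mean difference and its 95% confidence interval. Claim a decrease in all domains only if every domain shows a significant decrease. Because all must succeed, this claim needs no alpha adjustment.
3. Report the ratio of mean appropriate counts, post over baseline, with a patient-level bootstrap 95% interval beside the threshold. Do not use the Wilcoxon p-value as evidence that the threshold is met.
4. Keep the overall test for the main objective. Label any analysis added after the data were seen as post hoc; section 7.1 and Table 1 already report agreement results, so this may apply.

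**Cost.** SAP wording and a few hours of analysis, provided each recommendation carries a domain label, which the documents do not confirm for the counts. The stricter claim can lose power. If every domain is truly halved, the success rates (%) at means 0.1 / 0.25 / 0.5 / 1.0 are:

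| Claim | Independent | Linked |
|---|---|---|
| All 4 domains, one outcome | 1 / 8 / 46 / 94 | 25 / 99 / 100 / 100 |
| All 4 domains, both outcomes (taken as independent, so the rate is squared) | 0 / 1 / 21 / 88 | 6 / 98 / 100 / 100 |
| Both of 2 areas, one outcome | 5 / 27 / 68 / 96 | 52 / 99 / 100 / 100 |
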